8.2.4. Time Period and Frequency for Collecting/Reporting Adverse Event Information

The AE (both serious and nonserious) collection and AE reporting period begins with the signing of the ICF and continues until 6 months after the last dose of study medication. All AEs during this time period must be recorded whether or not the event is considered drug related.

For subjects who are screen failures, the active collection period for AEs ends when screen failure status is determined. Any SAEs occurring during screening procedures should be reported, and the appropriate causality assessment (ie, “not related” to study intervention) section of the SAE Report Form must be completed.

If the subject withdraws from the study and also withdraws consent for the collection of future information, the active collection period for AEs ends when consent is withdrawn.

Investigators are not obligated to actively seek information on AEs or SAEs after conclusion of the study participation. However, if the investigator learns of any SAE, including a death, at any time after a subject has been discharged from the study, and he/she considers the event to be reasonably related to the study intervention, the investigator must promptly notify PTC Pharmacovigilance Department via the SAE Report Form.

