1. INTRODUCTION AND OVERVIEW

The objective of this Statistical Analysis Plan (SAP) is to outline the procedures and statistical methods that will be employed to support the final reporting of Study PTC518-CNS-002-HD (PIVOT-HD) after the database lock for the double-blind treatment period. The statistical methods described here are based on Final Protocol Version 6.0, dated 05 October 2023. All decisions concerning the final analysis will be made before the database lock for the double-blind treatment period and the treatment unblinding and will be documented in this SAP.

This study will include a database lock for the double-blind treatment period and a final database lock. The database lock for the double-blind treatment period will occur after all subjects complete 12 months of treatment (Visit 8). The data collected during the double-blind treatment period will be included in the analysis and reported in the Clinical Study Report (CSR).

Specifically, the study assessments up to 30 days (i.e., 1-month safety follow-up) after 12 months of treatment (Visit 8) will be included in the double-blind treatment period. The final database lock will take place after all subjects have completed the study. Listings for the additional data collected beyond the double-blind treatment period will be provided and reported after the final database lock.

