3.4.6. Study Analysis Visit

Study analysis visits during the study will be derived as listed in [Table 2](#), based on study days from the randomization date. This window applies to scheduled, unscheduled, or early termination visits. The analysis visit number for each visit, including scheduled, unscheduled, repeat, and early termination/end of study visits, will be re-mapped. Study analysis visits will be used in all by-visit summaries for both efficacy and safety assessments wherever appropriate.

Table 2: Analysis Visit Windows

Analysis Visit	Target Study Day	Analysis Window (Study Day Range)
Visit 3 (Month 1)	30	16-45
Visit 4 (Month 2)	60	46-75
Visit 5 (Month 3)	90	76-120
Visit 6 (Month 6)	180	151-210
Visit 7 (Month 9)	270	241-300
Visit 8 (Month 12)	360	331- (last dose of study drug + 30 days)

For a given subject, if multiple assessments are within the same analysis window, the assessment at the scheduled visit will be used for the analysis; if the scheduled assessment is not available, the one closest to the scheduled study day and with non-missing value will be used for the analysis at that visit. In case of equal number of days to the scheduled visit date, the later assessment with non-missing value will be used for the analysis at that visit. In summary, the assessment to be used for the analysis is determined by the following order:

- 1) The assessment at the scheduled visit
- 2) The assessment closest to the target study day
- 3) The latter assessment, if ≥ 2 observations are equally close to the target study day

Any assessments occurring beyond the last dose of study drug + 30 days will be excluded from the analysis.

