6.1. Adverse Events

All AEs will be coded using the MedDRA Version 25.0. All AEs will be assigned a severity grade using Common Terminology Criteria for Adverse Events (CTCAE) Version 5.0 (refer to the study manual).

A treatment-emergent adverse event (TEAE) will be defined as an AE with onset date, or date of worsening if occurring prior to the first dose of study drug, between the date of first dose of study drug and the date of last dose of study drug + 30 days, inclusive. Only those TEAEs will be included in summary tables.

All AEs, treatment-emergent or otherwise, will be presented in subject data listings. An overview table of TEAEs, including number of subjects with TEAEs, treatment-emergent serious adverse events (TESAEs), TEAEs leading to discontinuation from study treatment, deaths, TEAEs by maximum severity, and treatment-related TEAEs, will be summarized by treatment group. A treatment-related AE will be defined as an AE with a relationship of possibly, probably, or related to the study treatment, as determined by the investigator.

In the summary tables, subjects may be counted under multiple SOCs and PTs, but for each SOC and PT, subjects are only counted once. If a subject has the multiple TEAEs in the same SOC or PT, the highest severity (5=fatal, 4=life-threatening, 3=severe, 2=moderate, 1=mild) recorded for the event will be presented and the closest drug relationship (1='Unrelated', 2='Unlikely to be Related', 3='Possibly Related', 4='Probably Related'), reclassified into Related ('Possibly Related', 'Probably Related') or Not Related ('Unrelated', 'Unlikely to be Related'), will be presented on the respective tables.

The following summaries will be produced for the TEAEs and TESAEs by treatment groups:

- TEAEs by SOC and PT
- TEAEs by PT (for cases where the incidence $\geq 5\%$ in either the 5 mg or 10 mg dose group)
- Treatment-related TEAEs by SOC and PT
- TEAEs by maximum severity
- TEAEs by relationship to study treatment
- TESAEs by SOC and PT
- Treatment-related TESAEs by SOC and PT
- TEAEs leading to discontinuation from study treatment by SOC and PT
- Treatment-related TEAEs leading to discontinuation from study treatment by SOC and PT

For the AE data the following rules will apply:

- For the derivation of treatment-emergent status (applicable to all AEs): If the start date/time of an AE is incomplete or missing, an AE will be assumed to be a TEAE,

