unless the incomplete start date/time or the end date/time indicates an AE started before dosing.

- For the derivation of treatment-related status (applicable to TEAEs only): If the study treatment relationship for a TEAE is missing, a TEAE will be assumed to be a treatment-related TEAE.
- For the calculation of TEAE summary statistics: If the severity of a TEAE is missing, that TEAE will be counted under the 'missing' category.

All AEs, deaths, SAEs and TEAEs leading to discontinuation from study treatment will be presented in by-subject data listings.

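### The SAP's incomplete-date rule for adverse events drops the upper bound of its own TEAE definition, so a month-only onset known to fall after last dose + 30 days is counted as treatment-emergent

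*SAP*

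**What the plan says.** SAP 6.1 (Adverse Events) gives the TEAE window two ends: onset, or worsening of an event already present, must fall "between the date of first dose of study drug and the date of last dose of study drug + 30 days, inclusive". The flag decides what is tabulated: "Only those TEAEs will be included in summary tables".

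The same section has a rule for incomplete start dates, stated to apply to all adverse events: "If the start date/time of an AE is incomplete or missing, an AE will be assumed to be a TEAE". The sentence goes on to name a single case in which this default is lifted; it applies "unless the incomplete start date/time or the end date/time indicates an AE started before dosing". No other exception is given.

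Protocol 8.2.4 sets the collection period, which "begins with the signing of the ICF and continues until 6 months after the last dose of study medication". Events after the TEAE window are therefore recorded by design.

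Two other SAP statements bear on reach. SAP 1 (Introduction and Overview) defines the double-blind period so that "the study assessments up to 30 days (i.e., 1-month safety follow-up) after 12 months of treatment (Visit 8) will be included"; data beyond it are only listed, after the final lock. SAP 3.4.6 (Study Analysis Visit) states: "Any assessments occurring beyond the last dose of study drug + 30 days will be excluded from the analysis".

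**The concern.** The definition has a lower and an upper bound, but the partial-date rule protects only the lower one. The SAP already accepts that the known part of a date can settle the matter before dosing. It does not apply the same logic after the window, so a less precise record of the same event gets a different classification from a precise one. That goes beyond caution about unknown dates, because it sets aside what the recorded month already shows.

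Safety against placebo is a primary objective (SAP 1.2.1). A misflagged event enters the TEAE tables and, where its attributes qualify, the serious and treatment-related tables. If its relationship to treatment is missing, SAP 6.1 also makes it treatment-related. Groups are small: about 24 subjects per dose in each of two stages, so 2 x 24 = 48 per dose. In the preferred-term table with a 5% cut-off, 2/48 = 4.2% is left out and 3/48 = 6.3% is shown, so one subject could decide whether a term appears.

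**Working it through.** The plan states no figure on this point, so there is none to reproduce. The check codes the two rules and compares them on dates.

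**Notation.** F = first dose, L = last dose; m1 and m2 = the earliest and latest days consistent with the recorded start date.

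- Definition: TEAE if F <= onset <= L + 30 days.
- Incomplete-date rule as written: not a TEAE if m2 < F (or the end date shows onset before dosing); otherwise a TEAE.
- Rule consistent with the definition: as above, and also not a TEAE if m1 > L + 30 days.

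**Illustration: a subject who stops early (assumed dates).** F = 10 Jan 2024, L = 15 Mar 2024, so the window closes on 14 Apr 2024.

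| Recorded onset | Days after last dose | Definition | Rule as written | With upper bound |
|---|---|---|---|---|
| Dec 2023 | before first dose | not TEAE | not TEAE | not TEAE |
| Feb 2024 | on treatment | TEAE | TEAE | TEAE |
| Apr 2024 | 17 to 46 | cannot tell | TEAE | TEAE |
| May 2024 | 47 to 77 | not TEAE | TEAE | not TEAE |
| Jun 2024 | 78 to 107 | not TEAE | TEAE | not TEAE |
| missing | unknown | cannot tell | TEAE | TEAE |

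The two versions differ only in the May and June rows, where every possible day is outside the window.

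**Can such records exist?** In this example collection runs to 15 Sep 2024. From 14 Apr to 15 Sep is 16 + 31 + 30 + 31 + 31 + 15 = 154 days, and five calendar months (May to September) begin in that stretch. Over every possible last-dose date in 2024 the stretch is 151 to 154 days, and five months begin in it for 358 of 366 dates. This shows that there is room for such records. It is not a share of events.

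**Which of them reach the tables?**

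- *Completers.* Take F = 16 Jan 2023 and L = 15 Jan 2024, with Visit 8 on the day of last dose. Both the TEAE window and the SAP 1 cut close on 14 Feb 2024. A Mar 2024 event is a TEAE by the written rule, but it lies beyond the cut and is only listed. If the cut is applied to adverse-event records, completers are largely protected.
- *Early stoppers.* In the first example, 12 months of treatment would have ended about 10 Jan 2025. Adding 30 days gives about 9 Feb 2025. Collection ended on 15 Sep 2024, so the whole follow-up precedes a cut counted from Month 12, and the June event can be tabulated.

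**Number affected.** Expected misflags = subjects x proportion stopping early x follow-up events each x share with month-only dates x share of those in a month wholly past the window and before the cut. The documents give none of the last four. Purely as an illustration, assume 5-15% stop early, 0.5-2 events each and 5-15% month-only dates. For the last term, assume stop times uniform over 12 months, onsets uniform over 180 days after last dose and a cut at Month 13; simulation then gives about 0.58. For the roughly 144 subjects planned in Parts A, B, D and E:

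- low: 144 x 0.05 x 0.5 x 0.05 x 0.58 = 0.1
- high: 144 x 0.15 x 2 x 0.15 x 0.58 = 3.8

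The spread comes entirely from the assumptions.

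**The case against.** The best case against acting is that other SAP text already prevents the problem.

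- The SAP 1 cut makes late data listing-only. This largely stands for subjects who complete 12 months. For early stoppers, Protocol 4.4 calls the Early Termination Visit Visit 8, and the schedule of assessments puts it in the same column, so the 30 days could be read as running from that visit. The reading is possible but not secure: SAP 1 ties Visit 8 to 12 months of treatment, and Protocol 4.4 also expects evaluations to continue on the original schedule after drug is stopped.
- SAP 3.4.6 counts from last dose and would reach early stoppers. But it concerns assessments mapped to analysis visits, while SAP 6.1 gives adverse events a rule of their own. At most it shows the intended cut-off.

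The default is also conservative, safety summaries are descriptive (Protocol 9.3.2), no test depends on the flag, onset date is a required field (Protocol 8.2.3), and all events are listed by subject. All of this stands and limits the importance of the point. It does not make the rule agree with the definition.

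A reader might infer more in two ways:

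- *A large share of post-treatment events is misclassified.* About 150 of 180 follow-up days (83%) lie outside the window, and with uniform onsets about 75% of month-only records would fall in a month wholly past it. Those shares ignore the SAP 1 cut, and they describe only month-only records, whose number is unknown.
- *The active arms are inflated relative to placebo.* That needs more early stopping on PTC518, for which the documents give no evidence.

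**Conclusion.** The point holds as a drafting error of minor consequence. Read literally, SAP 6.1 classifies as treatment-emergent an event that its own definition excludes, whenever the recorded month and year lie wholly after last dose + 30 days. This follows from the text and needs no assumption.

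The effect is mainly confined to subjects who stop treatment early, provided the SAP 1 cut is applied to adverse-event records. The number of records cannot be computed from the documents; it is probably small and may be zero, and the illustrative range above is not an estimate. The direction is over-counting of TEAEs. No effect on the comparison between arms, and none on any efficacy conclusion, can be claimed.

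**What to change.** In the incomplete-date rule of SAP 6.1, keep the existing exception and add a second: the event is also not a TEAE if the known parts of its start date show onset after the last dose of study drug + 30 days. State that fully missing dates, and months that straddle the bound, remain TEAEs, so that the conservative default is kept wherever timing is really unknown.

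The cost is one clause in the SAP and one condition in the derivation program, with no new data. TEAE counts may fall by a few events.

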6.2. Laboratory Values

Blood samples for hematology, clinical chemistry, and urinalysis will be collected at the visits defined in protocol and the test results will be presented in standard units. The continuous test results and change from baseline will be descriptively summarized by visit and treatment group. Laboratory parameters that will be assessed will include:

- Hematology: hemoglobin, hematocrit, red blood cell count (RBC), platelet count, white blood cell count (WBC), WBC differential, neutrophils, eosinophils, monocytes, basophils, and lymphocytes
- Clinical chemistry: albumin, alkaline phosphatase, alanine aminotransferase, aspartate aminotransferase, bicarbonate, total bilirubin, direct bilirubin, indirect bilirubin, calcium, chloride, total cholesterol, creatinine, gamma-glutamyl transpeptidase, glucose, high-density lipoprotein, low-density lipoprotein, lactate dehydrogenase, potassium, sodium, total protein, triglycerides, urea, and uric acid
- Urinalysis: albumin, bilirubin, erythrocytes, glucose, ketones, leukocyte, microscopy, nitrite, pH, specific gravity and urobilinogen
- Coagulation: PT (sec), PT (INR), aPTT

Clinical laboratory test results will be assigned a Low/Normal/High (L/N/H) classification according to whether the value is below (L), within (N), or above (H) the laboratory parameter's reference range. Shifts from baseline to each post-baseline visit will be provided for each laboratory parameter by treatment group.

Abnormal laboratory test results (i.e., results assigned as L/H) will be listed in a by-subject data listing.

CSF assessments, which include WBC, RBC, protein, and glucose, will be gathered locally. These measurements will subsequently be converted to standard units. The test results for WBC and protein will be descriptively summarized by visit and treatment group.

6.3. NfL Levels in Plasma and CSF

For NfL, blood and CSF samples will be collected pre-dose at Visit 2 (baseline) and subsequent post-baseline visits. The samples will be analyzed by the same bioanalytic laboratory as blood tHTT protein. For the same reason as blood tHTT protein, a sample may have multiple results.

For the analysis purpose, a single result at baseline and at each post-baseline visit will be derived according to the following steps:

1. The change and percent change from baseline will be calculated for each post-baseline visit using the baseline result from same run.
2. For each subject, the result from the last run will be used for the analysis for both baseline and post-baseline visits.

These safety exploratory endpoints will be summarized descriptively by treatment group for each visit.

6.4. Vital Signs and Weight

Vital sign measurements (including blood pressure, pulse rate, respiration rate, body temperature and oxygen saturation) and weight (and BMI), and the change from baseline will be summarized descriptively by visit and treatment group.

The vital sign measurements and weight (and BMI) will be presented in a by-subject data listing.

6.5. Physical Examination

Abnormal physical examination results will be listed in a by-subject listing.

6.6. 12-Lead Electrocardiogram (ECG)

The ECGs parameters (including heart rate, RR interval, PR interval, QRS interval, QT interval, Corrected QT interval using Bazett's formula [QTcB] and Corrected QT interval using Fredericia's formula [QTcF]) and the change from baseline will be summarized descriptively by visit and treatment group. The ECGs will be performed in triplicate. For the above ECG parameters, the averaged value of the triplicate will be used for the analysis. For the overall interpretation of ECG (normal, abnormal clinically significant, or abnormal not clinically significant), the value that represents the greatest degree of abnormality will be used for the analysis. In addition, shift from baseline to each post-baseline visit in the overall interpretation will be provided by treatment group.

Categorical analysis of the maximum post-baseline value in QTcF interval will be performed to summarize the number and percentage of subjects meeting the criteria below.

- Absolute QTcF interval prolongation:
 - QTcF interval \leq 450 ms
 - QTcF interval > 450 and ≤ 480 ms
 - QTcF interval > 480 and ≤ 500 ms
 - QTcF interval > 500 ms
- Change from baseline in QTcF interval:
 - QTcF interval increases from baseline ≤ 30 ms
 - QTcF interval increases from baseline > 30 and ≤ 60 ms
 - QTcF interval increases from baseline > 60 ms

A by-subject listing of ECG results will be provided.

[figure not shown]
6.8. Columbia Suicide Severity Rating Scale (C-SSRS)

The Columbia-Suicide Severity Rating Scale (C-SSRS) is a measure used to identify and assess individuals at risk for suicide. The C-SSRS summary will display the number and percentage of subjects who report “Yes” to specific C-SSRS items or categories of items (a category is assigned a “Yes” value if a “Yes” is reported for any item in the category) descriptively by visit and treatment group. These C-SSRS items and categories are as follows:

- Suicidal Ideation Items
 - (1) Wish to be dead
 - (2) Non-specific active suicidal thoughts
 - (3) Active suicidal ideation with any methods (not plan) without intent to act
 - (4) Active suicidal ideation with some intent to act, without specific plan
 - (5) Active suicidal ideation with specific plan and intent
- Suicidal Behavior Items (not reported for the Screening/past 1 year assessment)
 - (6) Preparatory acts or behavior
 - (7) Aborted attempt
 - (8) Interrupted attempt
 - (9) Non-fatal suicide attempt
 - (10) Completed suicide
- Suicidal Behavior Category: Any of items (6) through (10)
- Non-Suicidal Self-Injurious Behavior

In addition to the summaries described above, the shift from baseline to each post-baseline visit in suicidal ideation and behavior (categorized as (1) No Suicidal Ideation or Behavior, (2) Suicidal Ideation only, and (3) Suicidal Behavior will be provided by visit and treatment group.

The C-SSRS results will be provided in by-subject data listings.

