Subjects will return to the clinic every month until Visit 5 (Month 3) and then quarterly until Visit 8 (Month 12). Upon completion of Visit 8 (Month 12), subjects will have the option to enroll in Study PTC518-CNS-004-HD, a Phase 2 long-term extension study, to receive PTC518.

For subjects not enrolling in Study PTC518-CNS-004-HD, Visit 8 will be considered the End of Treatment visit, and there will be a Follow-Up Safety Visit (Month 13) via telephone/telehealth to collect adverse event data and an additional Follow-Up Safety Visit on Month 16 (ie, approximately 4 months after the last dose of study drug) to collect adverse events [REDACTED]. A final Follow-Up Safety Visit will occur on Month 18 via telephone/telehealth to collect adverse event data.

Sample Size Justification:

The sample size calculation for each disease stage is based on mean change from Baseline in blood tHTT protein at Month 3 (primary endpoint) assuming PTC518 has the same effect on blood tHTT protein reduction. With an effect size of 0.85 (ie, the magnitude of treatment difference is 85% of one standard deviation), achievement of 85% power at 2-sided alpha level 0.05 would require 24 subjects. Approximately 24 subjects will be randomized to each active treatment arm and approximately 36 additional subjects per disease stage will be randomized to placebo. An additional 18 subjects (per disease stage) may be randomized to the maximum tolerated dose.

Number of Subjects (Planned):

Up to 252 adult male and female subjects (126 per disease stage) will be enrolled.

Diagnosis and Main Criteria for Inclusion:

Individuals eligible to participate in this study include those who meet all of the following inclusion criteria:

1. Ambulatory male or female patient aged 25 years and older, inclusive
2. Subject is willing and able to provide informed consent and comply with all protocol requirements.
3. Genetically confirmed HD diagnosis with a cytosine-adenine-guanine (CAG) repeat length from 40 to 50, inclusive. CAG repeat length may be determined analytically through amplification.

Eligibility for HD-ISS Stage 2 Group (Parts A, B, and C)

4. A UHDRS IS score of 100
5. A UHDRS TFC score of 13
6. A score between 0.18 and 4.93 inclusive on the normed version of the HD prognostic index (PIN_{HD})

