Adverse events	X	X	X	X	X	X	X	X	X	X	X	X	Safety follow-up at Visit 9 may be done by telephone/telehealth. Information about AEs will be collected from the signing of consent through 6 months after the last dose of study medication.
C-SSRS	X	X		X	X	X	X	X	X				The “Baseline” version of the C-SSRS version will be used at Screening and Baseline. The “Since Last Visit” version of the C-SSRS will be used at all other timepoints.

Abbreviations: AE, adverse event; CAG, cytosine-adenine-guanine; CSF, cerebrospinal fluid; C-SSRS, Columbia Suicide Severity Rating Scale; ECG, electrocardiogram; eCRF, electronic case report form; EOS, end of study; EOT, end of treatment; ET, Early Termination; FuRST 2.0, Functional Rating Scale; HCG, human chorionic gonadotropin; HTT, huntingtin (protein); HTT, huntingtin (gene); IS, Independence Scale; NfL, neurofilament light chain; PBA-s, short form of the Problem Behaviors Assessment; PIN_{HD}, normed version of the Huntington’s disease prognostic index; PK, pharmacokinetics; SDMT, Symbol Digit Modalities Test; TFC, Total Functional Capacity; TMS, Total Motor Scale; [REDACTED]; TUG, Timed Up and Go; UHDRS, Unified Huntington’s Disease Rating Scale; vMRI, volumetric magnetic resonance imaging; WOCBP, women of childbearing potential

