3.4.2. Baseline Definitions and Change from Baseline

For all efficacy and PD endpoints, unless otherwise specified, the assessments collected at the randomization date will serve as the baseline value. If the randomization visit value is not available, then the last non-missing assessment collected prior to randomization will serve as the baseline. For safety endpoints, the baseline value is defined as the last non-missing assessment prior to the first study drug administration.

For the analysis purposes, change from baseline and percent change from baseline will be derived as follows:

$$\text{Change from baseline} = \text{Post-baseline value} - \text{Baseline value}$$

$$\text{Percent change from baseline} = 100 \times (\text{Post-baseline value} - \text{Baseline value}) / \text{Baseline value}$$

For the vMRI assessments, where the change is directly measured using the Boundary Shift Integral (BSI) for multiple brain areas, the change will not be calculated. For more details, please refer to Section [3.4.3](#).

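### SAP 6.8 summarizes the C-SSRS only visit by visit, over recall periods of unequal length, and gives no per-arm count for the whole treatment period

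*SAP*

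**What the plan says.** Protocol Table 4 (Section 3.7) fixes the forms. The 'Baseline' "version of the C-SSRS version will be used at Screening and Baseline", and the 'Since Last Visit' "version of the C-SSRS will be used at all other timepoints". The protocol synopsis sets visits monthly up to Visit 5 (Month 3) and quarterly from there to Visit 8 (Month 12).

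SAP 6.8 plans three C-SSRS outputs:
- the number and percentage answering 'Yes' to each item or category, by visit and arm;
- "the shift from baseline to each post-baseline visit in suicidal ideation and behavior", in three categories (neither, ideation only, behavior);
- by-subject listings.

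The starting category comes from SAP 3.4.2: "For safety endpoints, the baseline value is defined as the last non-missing assessment prior to the first study drug administration". Neither document states the recall period of the pre-dose form. The only hint is in SAP 6.8, where the behavior items are "not reported for the Screening/past 1 year assessment".

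SAP 3.4.6 governs which assessment enters a by-visit table. A scheduled assessment takes precedence over any other in the same window, and the Table 2 windows also apply to unscheduled and early-termination visits. Protocol 3.7 allows a C-SSRS at unscheduled visits at the investigator's discretion.

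**The concern.** A 'Since Last Visit' answer describes the interval since the previous visit, so its chance of being 'Yes' depends on the length of that interval. The interval lengthens after Month 3. A reader who follows one arm across the by-visit table is comparing periods of different length, and a rise after Month 3 need not mean a rise in risk.

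The shift table has a related weakness. Its starting point is a different form with an unstated recall. A subject placed in the ideation category before dosing who reports ideation again on treatment sits on the diagonal, as no change. A subject placed in the behavior category who reports ideation on treatment appears to have improved.

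The C-SSRS is a named safety endpoint under a primary safety objective. The natural question is how many subjects in each arm had any suicidal ideation, or any suicidal behavior, while on treatment. No planned C-SSRS table answers it.

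**Working it through.** The documents give no C-SSRS rate, so there is no plan figure to reproduce. Every rate below is an assumption, shown as a range.

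**1. Look-back length.** The target days in SAP Table 2 are 30, 60, 90, 180, 270 and 360. Successive differences, starting from Day 1, are 29, 30, 30, 90, 90 and 90 days. The interval ratio after Visit 5 is 90/30 = 3.0. If the last pre-dose C-SSRS falls in Days -22 to -1, with none on Day 1 (how Table 4 reads, though its layout may be broken), the Visit 3 answer reaches back 30 to 51 days and includes pre-dose days. The Visit 6 to Visit 3 ratio is then 90/51 = 1.8 to 90/30 = 3.0.

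**2. Effect on the 'Yes' rate at constant risk.** Let p be the chance of a 'Yes' in one month. The chance of any 'Yes' in three months is at least p and at most 3p, so the ratio lies between 1 and 3. Two models show where it falls.

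Independent months, 1 - (1 - p)^3:

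| p | 3-month rate | Ratio |
|---|---|---|
| 1% | 2.97% | 2.97 |
| 5% | 14.26% | 2.85 |
| 20% | 48.80% | 2.44 |

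Persistent ideation, with monthly prevalence π and month-to-month persistence s. The monthly onset chance is a = π(1 - s)/(1 - π), and the 3-month rate is 1 - (1 - π)(1 - a)^2. With π = 5%:

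| s | 3-month rate | Ratio |
|---|---|---|
| 0.30 | 11.87% | 2.37 |
| 0.50 | 9.93% | 1.99 |
| 0.80 | 6.99% | 1.40 |
| 0.95 | 5.50% | 1.10 |
| 1.00 | 5.00% | 1.00 |

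**3. Recurrence in the shift table.** Let h be the share of subjects in the ideation category at baseline, and r their risk of on-treatment ideation relative to the others. The share of on-treatment ideation that does not appear as an upward shift is hr / [(1 - h) + hr].

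| h | r = 1 | r = 3 |
|---|---|---|
| 0% | 0% | 0% |
| 5% | 5% | 14% |
| 10% | 10% | 25% |
| 20% | 20% | 43% |
| 30% | 30% | 56% |

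**4. Whether by-visit counts give the total.** They do not, because one subject can answer 'Yes' at several visits. Suppose an arm shows 2 subjects with 'Yes' at each of the six post-baseline visits. The number of distinct subjects could be anything from 2 (the same two each time) to 6 × 2 = 12.

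**5. Assessments that reach no summary table.** SAP Table 2 covers Days 16-45, 46-75, 76-120, 151-210, 241-300 and 331 onward. An unscheduled or early-termination C-SSRS before Day 16, or on Days 121-150, 211-240 or 301-330, maps to no visit. Inside a window, an unscheduled 'Yes' is set aside when a scheduled assessment exists. If the scheduled form then counts from the unscheduled visit, which the documents do not settle, that event appears in no C-SSRS summary table.

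**The case against.** The strongest reply is that the planned comparison is unaffected. The objective is safety compared with placebo, look-back is scheduled alike in every arm, and the output is descriptive with no test. Any artefact of interval length appears in the placebo arm as well. This stands: same-visit contrasts between arms are fair, and type I error and power are not involved.

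A second reply is that the shift table is not the only display. Recurrence on its diagonal is still counted as a 'Yes' by item, visit and arm, and it is listed by subject. Events that meet the adverse event definition also enter the SAP 6.1 tables, which run to 30 days after the last dose. This stands for every assessment that enters a by-visit table. It does not supply the per-arm C-SSRS count, and listings carry no arm totals.

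Third, exclusion criterion 9 removes subjects rated at moderate or higher C-SSRS risk, so baseline positives should be limited. That is fair, and it argues for the lower rows of h above. It does not make h zero, because lower ratings remain eligible.

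Fourth, SAP 7 places the table shells in a separate document, so a look-back footnote may already exist there. That cannot be checked. The absence of a whole-period summary from SAP 6.8 can be.

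**Conclusion.** The point holds as a limitation of the display that is cheap to repair. By-visit percentages cannot be read as a time trend: at constant risk the change after Month 3 lies between no inflation and just under threefold, and the documents give no rate or persistence to place it more closely. The shift table can miss recurrence in baseline-positive subjects. The main gap is that no table counts subjects with ideation or behavior over the whole treatment period, and some 'Yes' answers can fall outside every summary table.

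Three stronger readings are tempting and not supported:
- That 'Yes' rates triple by construction. The interval triples. The rate approaches a threefold rise only for rare events that are independent from month to month.
- That the shift table hides new suicidality on treatment. Ideation in a subject with none at baseline, and a move from ideation to behavior, both register as upward shifts.
- That a long baseline recall produces a steep artificial fall by Month 1. This needs a recall period for the Baseline visit that neither document gives. The one-year wording is tied to Screening and sets the behavior items aside, and the entry restriction on C-SSRS risk would have to be ignored.

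The SAP already summarizes other safety data over the whole period: SAP 6.6 uses the maximum post-baseline QTcF, and SAP 6.1 uses maximum severity. The C-SSRS has no equivalent.

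**What to change.** In SAP 6.8, keep the by-visit tables and add, per arm:

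1. The number and percentage of subjects with any on-treatment suicidal ideation, and separately with any on-treatment suicidal behavior, regardless of history. This captures recurrence that a shift table leaves on its diagonal.
2. One shift table from the pre-dose category to the worst on-treatment category.

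Both should use all on-treatment assessments, including unscheduled and early-termination ones, whether or not they fall in a Table 2 window. The SAP should also state which recall period of the pre-dose form supplies the baseline category, and footnote each form's look-back, including that the Visit 3 answer may reach into pre-dose days.

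The cost is one or two extra tables plus SAP wording and shells. No new data are needed. Pooling Visits 3 to 5 into one three-month interval is optional and not required.
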